### **Study Aims and Hypotheses**

The goals of the study will be as follows:

- 1. To examine the perceived acceptability, usefulness, and client satisfaction following participation in the Single-Session Consultation (SSC) service at the Krasner Psychological Center (KPC) and Mind Body Clinical Research Center (MBCRC) among waitlisted adolescent and adult clients
- 2. To examine therapists' perceived acceptability, feasibility, and effectiveness of the single session consultation at three time points: pre-training, post-training, and post-SCC administration
- 3. To assess the demand for and feasibility of providing the SSC service at the Krasner Psychological Center and Mind Body Clinical Research Center (i.e., documenting the proportion of clients who choose to participate in the service when it is offered; documenting the number of sessions successfully completed, rescheduled, and/or cancelled).
- 4. To assess whether levels of proximal clinical outcomes (e,g, hope, agency) are improved immediately following completion of the SSC, both in adolescent and adult clients.
- 5. To assess whether levels of psychological symptoms are improved two weeks following completion of the SSC, both in adolescent and adult clients.
- 6. To assess rates of (a) remaining on the clinic waitlist for therapy and (b) length of subsequent treatment at the Mind Body Clinical Research Center and Krasner Psychological Center among individuals participating in the SSC, relative to clients who sought out services in the six months prior to the SSC being offered to clients (January June 2019).

Hypotheses associated with each of these aims will be as follows:

- 1. Clients' proximal clinical outcomes (e,g, hope, measured by the Beck Hopelessness Scale 4 item version, and Agency, measured by the State Hope Scale; both primary study outcomes), which are hypothesized to serve as mechanisms for intervention effects, will improve from immediately pre-SSC completion to immediately post-SSC.
- 2. Adolescent and adult clients will perceive the SSC at the Mind Body Clinical Research Center and Krasner Psychological Center as acceptable and useful in addressing their clinical needs, indexed by mean ratings of at least 3.5 out of 5 across the five items on the "Consultation Feedback Form".

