- 3. The SSC will show feasibility as a model for service provision at the Mind Body Clinical Research Center and Krasner Psychological Center (i.e., a majority [>50%] of clients who are offered the SSC service will elect to receive it, and most [>75%] of clients who schedule an SSC appointment will attend)
- 4. Clients' overall psychological symptom levels will reduce two weeks after the SSC, relative to symptoms immediately prior to the SSC

- 5. No prediction is made about therapists' perceived acceptability, feasibility, and effectiveness of single session interventions at baseline or their subsequent assessment, given the novelty of research in this domain.
- 6. Clients who receive the SSC will be less likely to remain on the clinic wait list—and, among those who elect to remain on the clinic wait list, total therapy duration will be briefer—relative to clients who sought service at the Mind Body Clinical Research Center and Krasner Psychological Center prior to the SSC service being offered.

Note that data will be available for testing hypotheses 1-5 substantially sooner than for testing hypothesis 6, as the duration of clients' potential future psychotherapy at the Krasner Psychological Center and Mind Body Clinical Research Center is impossible to determine. Whereas data for the first four hypotheses will be available two weeks subsequent to recruitment completion, data for the fifth hypothesis may be unavailable for up to a year subsequent to recruitment completion. Accordingly, the authors may report results from hypotheses 1-5 in a manuscript or conference presentation prior to completion of data collection for hypothesis 6, noting that data relevant to hypothesis 6 will be reported at a to-be-determined future date. Data relevant to hypothesis 6 (which requires extraction of aggregate client information associated with previous Mind Body Clinical Research Center and Krasner Psychological Center clients) will not be collected, and thus will remain unknown to investigators, until all relevant data are available for analysis (i.e., until all clients who completed the SSC and chose to receive full-length psychotherapy have terminated their course of treatment at the clinic).

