## **Analytic Plan**

To address Hypothesis 1, we will conduct two 2-tailed paired samples t-tests to assess whether participants scores on the Beck Hopelessness Scale – 4 item version and the State Hope Scale, respectively, significantly reduced from pre-SSC to post-SSC. A pre-post difference with a p value of < .05 will indicate a significant change in hope, agency, from pre-SSC to post-SSC. To address Hypothesis 2, we will examine mean scores on the "Consultation Feedback Form," which contains 5 items rated on a 1-5 Likert scale by participants (e.g., "Did you find the consultation helpful in addressing your concern(s)?"; "How motivated do you feel to use your action plan?") A mean score of 3.5 out of 5 or higher across participants in this study would indicate participants found the SSC more than somewhat helpful in addressing their concerns.

To address Hypothesis 3, we will first divide the number of people who accepted the Mind Body Clinical Research Center and Krasner Psychological Center's invitation to take part in the SSC service (whether or not they subsequently attend their scheduled session) by the number of people who declined the invitation to take part in the SSC service. We will then divide the number of people who attended their scheduled SSC session by the total number of people who scheduled an SSC session, regardless of future attendance. If the first number exceeds .5 (50%), and the second number exceeds .75 (75%), we will conclude the SSC's feasibility as a service delivery model.

To address Hypothesis 4, we will again use a 2-tailed paired samples t-test to assess whether participants' brief symptom inventory score significantly reduced from pre-SSC to follow-up. A pre to follow-up difference with a p value of < .05 will indicate a significant change.

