We will use maximum likelihood estimation to address any item- and subject-level missing data that may emerge.

The false discovery rate (FDR) will be applied to identify potential false-positive results. Q-values will be computed for p-values from t tests using an online calculator applying Benjamini and Hochberg's (1995) approach (https://www.sdmproject.com/utilities/?show=FDR). Results will be considered significant if FDR corrected q < 0.05 (incurring maximum 5% false-positive rate amongst all tests meeting significance at p < 0.05). Both p and q values will be reported.

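### Maximum likelihood is promised for missing clients, but the pre-post tests and the FDR p-values are fixed as t-tests, so a client without a two-week score is either dropped or tested as a filled-in value

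*SAP*

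**What the plan says.** All the relevant statements are in the SAP, mostly under Analytic Plan.

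- Missing data: "We will use maximum likelihood estimation to address any item- and subject-level missing data that may emerge". No model, variables, imputation step or standard-error method is named.
- Primary outcomes (hopelessness and agency): "To address Hypothesis 1, we will conduct two 2-tailed paired samples t-tests". Under Study Aims and Hypotheses these scores "will improve from immediately pre-SSC completion to immediately post-SSC".
- Two-week symptoms: "To address Hypothesis 4, we will again use a 2-tailed paired samples t-test to assess whether participants' brief symptom inventory score significantly reduced" between the pre-session and follow-up assessments, judged at p < .05.
- Multiplicity: "Q-values will be computed for p-values from t tests using an online calculator", with significance declared at q < 0.05.
- Reporting order: "the authors may report results from hypotheses 1-5 in a manuscript or conference presentation" before the Hypothesis 6 data are complete.

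Sample Size Justification sets 40 clients and gives no expected loss to follow-up.

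**The concern.** A paired t-test is computed from within-client differences. If one of the two scores is absent there is no difference, and the test has no likelihood step that could use the score that is present. If the test stays a t-test, two routes remain for a client with a baseline but no follow-up score:

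- **(a) Drop the client.** The subject-level promise then has no effect on the test. If loss depends on the baseline score, the estimated change is biased, in a direction set by who is lost.
- **(b) Fill in the follow-up score** with its maximum-likelihood prediction and run the t-test on 40 pairs. Predicted scores carry no residual scatter and are counted as full observations, so the standard error is too small.

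A third route, testing the mean change directly from the likelihood estimates, is valid. It is not a t-test on scores, and the plan's wording on both the tests and the FDR inputs does not provide for it.

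The exposed test is Hypothesis 4. Hypothesis 1 is measured immediately before and after one session and should lose few pairs. Item-level gaps are not the difficulty: completing a few items before scoring is compatible with a t-test.

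What is at stake is the two-week symptom estimate in a pilot meant to inform a larger trial, and an analysis choice that could be made after the data are seen.

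**Working it through.** **Inputs.** From the SAP: 40 clients, two-sided 0.05, paired t-tests, q < 0.05. Assumed, because the SAP gives none of them: bivariate normal scores in SD units, pre/follow-up correlation r of 0.5 to 0.7, and 5% to 30% of follow-up scores missing. The SAP gives no inputs from which the figure of 40 could be rebuilt, and this point does not depend on it.

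**Why route (b) understates the error.** Take r = 0.6, N = 40 and n = 32 observed pairs (20% missing), with loss completely at random.

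- Variance of the estimated mean change, approximately: (1 - r²)/n + (1 - r)²/N = 0.64/32 + 0.16/40 = 0.0240, so SE = 0.155.
- Variance the t-test reports on the filled-in scores, approximately: [(1 - r)² + (n/N)(1 - r²)]/N = (0.16 + 0.8 × 0.64)/40 = 0.0168, so SE = 0.130.
- The reported SE is 0.130/0.155 = 0.84 of the true one. The nominal critical value of 2.02 then acts like about 1.69, a two-sided error near 9% before small-sample terms, which this approximation leaves out.

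**Simulated type I error, route (b)** (no true change, loss completely at random, 40,000 trials per cell):

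| Missing | r = 0.5 | r = 0.6 | r = 0.7 |
|---|---|---|---|
| 5% | 6.0% | 6.0% | 6.1% |
| 10% | 7.0% | 7.5% | 7.2% |
| 15% | 8.5% | 8.7% | 9.2% |
| 20% | 10.1% | 10.4% | 10.9% |
| 30% | 14.0% | 14.9% | 15.4% |

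Under the same loss, complete pairs give 4.8-5.1% and a direct likelihood test of the change gives 4.6-4.8%. Repeat simulations gave 9.7-10.7% for route (b) at 20% missing and 14.1-15.2% at 30%.

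**Bias, route (a).** The mean change among retained clients is δ - (1 - r)m, where δ is the true change and m is the retained clients' mean baseline relative to all clients. Simulated with r = 0.6, δ = -0.30 and logistic loss on baseline (20,000 trials per cell; ranges run from log-odds 0.5 to 1.0 per SD):

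| Missing | High scorers lost | Low scorers lost |
|---|---|---|
| 10% | -0.281 to -0.264 | -0.318 to -0.336 |
| 20% | -0.263 to -0.230 | -0.338 to -0.369 |
| 30% | -0.244 to -0.197 | -0.357 to -0.402 |

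The value -0.230 corresponds to m = -0.175: -0.30 + 0.4 × 0.175 = -0.23. The likelihood-based estimate stays between -0.297 and -0.302 throughout.

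Route (a) can also distort significance. With no true change and high scorers lost at log-odds 1.0 per SD, type I error is 5.9%, 7.0% and 9.0% at 10%, 20% and 30% missing. Under a different assumed pattern, also with high scorers lost more often, it is 6-7%, 9-11% and 11-16%.

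**The routes disagree on the same data.** With 20% missing, a true change of -0.30 and high scorers lost (log-odds 1.0), the chance of significance is about 30% by route (a), 60% by route (b) and 44% with the likelihood test.

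**Does FDR contain it?** If Hypotheses 1-5 are reported first, the client t-tests supply three p-values. With both Hypothesis 1 tests significant, the Benjamini-Hochberg cut-off for Hypothesis 4 is 0.05 × 3/3 = 0.05. At 20% missing, the route (b) error is then 10.0%, 10.4% and 10.8% for r = 0.5, 0.6 and 0.7, in effect unchanged. With all five t-tests in the family and both Hypothesis 6 tests null, the cut-off for a third-ranked p-value is 0.05 × 3/5 = 0.03. The error is then 7.1-7.7%, against 3.1% with complete data.

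**Item-level gaps.** Maximum-likelihood completion on a 4-item scale gave type I error of 4.6%, 5.1% and 5.7% at 2%, 5% and 10% of items missing. With 1,500 trials the Monte Carlo standard error is about 0.6 points, so none of these is distinguishable from 5%.

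**The replacement model.** On one complete data set, REML with unstructured covariance gave the paired t-test's estimate and standard error exactly (-0.4179, SE 0.1021). With degrees of freedom equal to complete pairs minus 1, its type I error was 5.3%, 5.4% and 5.0% at 10%, 20% and 30% missing (3,000 trials).

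**The case against.** The strongest reply is that this is under-specification. The missing-data sentence can be read as saying that a likelihood model takes over when data go missing, and that model equals the paired t-test when they do not. The SAP nowhere says that predicted scores will be filled in, so the inflation figures belong to a procedure it does not name. This does not remove the conflict. On the generous reading, the sentences on the tests and on the FDR inputs are both wrong as written and need rewording.

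Other points stand as limits:

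- Every size depends on assumed loss and correlation. Follow-up is only two weeks, and at 5-10% missing route (b) gives about 6-7.5%. The error doubles only from about 20% missing.
- Complete pairs are unbiased and hold 5% if loss is completely at random. At 10% missing the bias is 0.02-0.04 SD, against a standard error near 0.15 SD.
- Hypothesis 4 is not a primary outcome, and the study is a pilot.
- Inflation passing through FDR unchanged needs the three-test family with both Hypothesis 1 tests significant. The five-test family dilutes it.
- The simulated degrees of freedom were complete pairs minus 1, not Kenward-Roger or Satterthwaite.

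**Conclusion.** The concern holds. The plan commits to maximum likelihood for missing clients and then fixes tests, and a source of p-values, that cannot carry it out. That inconsistency does not depend on any assumption.

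Its effect depends on how many two-week scores are missing, which of the two routes is taken and, for dropping, who is lost. It is minor at 5% missing. From about 20% it is material: about double the nominal type I error if scores are filled in, or a change over- or understated by up to about 23% (0.07/0.30) if clients are dropped and loss follows baseline as assumed. It should be corrected, but it does not threaten the primary hypothesis.

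**What to change.** 1. **Hypothesis 4, and Hypothesis 1 for consistency:** replace the paired t-test with a REML repeated-measures model. Use time as a fixed effect, an unstructured 2×2 covariance, all available scores, and Kenward-Roger or Satterthwaite degrees of freedom. Report the mean change with its 95% confidence interval.
2. **Items:** state separately how missing items are handled before scoring. For example, use maximum-likelihood (EM) completion only if at least 75% of that scale's items are answered; otherwise the score is missing and left to the model.
3. **FDR:** reword the input so that it takes this model's p-values for Hypotheses 1 and 4.
4. **Sensitivity:** keep the complete-pair t-test and report the number of pairs.

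The cost is about three SAP sentences and a few lines of code, with no extra data. The model assumes that scores are missing at random given those observed.

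A smaller change would also remove the contradiction: state that the t-tests use complete pairs, withdraw the subject-level promise and report the number of pairs. That leaves the bias of route (a) in place.

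### The SAP sets two significance rules for its primary outcomes (p < .05 and FDR q < 0.05) and attaches the FDR's 5% bound to the wrong set of tests

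*SAP*

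**What the plan says.** Under Study Aims and Hypotheses, the two Hypothesis 1 measures (the four-item Beck Hopelessness Scale and the State Hope Scale) are "both primary study outcomes". The Analytic Plan gives each hypothesis its own criterion:

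- Hypothesis 1: "A pre-post difference with a p value of < .05 will indicate a significant change in hope, agency, from pre-SSC to post-SSC".
- Hypothesis 4: "A pre to follow-up difference with a p value of < .05 will indicate a significant change".
- Hypothesis 6: two independent-samples t-tests, also read at p < .05, but the SAP says only that such a result would be suggestive.

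The last paragraph of the Analytic Plan then adds a general rule. Its purpose is given as "The false discovery rate (FDR) will be applied to identify potential false-positive results". Its scope is "Q-values will be computed for p-values from t tests", with no test excepted. Its criterion is "Results will be considered significant if FDR corrected q < 0.05", and its error rate is described as "incurring maximum 5% false-positive rate amongst all tests meeting significance at p < 0.05". It ends with "Both p and q values will be reported".

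**The concern.** There are two separate faults.

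First, the same three tests (two primary, one for Hypothesis 4) have two decision rules. The Hypothesis 1 and 4 sentences are unconditional and do not point forward to the FDR paragraph. That paragraph does not say that it replaces them. A report calling a primary result with p = .04 significant would follow the Hypothesis 1 text exactly and could still breach the FDR text. A prespecified plan should not leave that choice open until the data are seen.

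Second, the stated error rate belongs to a different set of tests. Benjamini-Hochberg bounds the expected proportion of false positives among tests declared at q < 0.05. The SAP gives that bound to all tests with p < 0.05, a set that is at least as large and usually larger. A reader who relies on it would credit every p < .05 result with a protection it does not have.

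**Working it through.** **Inputs from the SAP.** 40 clients (Sample Size Justification). Five named two-sided t-tests: two for Hypothesis 1, one for Hypothesis 4, two for Hypothesis 6. Thresholds p < .05 and q < 0.05 (Analytic Plan).

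**Assumptions not in the SAP.** It gives no effect sizes, correlations between tests or FDR family. I take the three Hypothesis 1 and 4 tests as the family unless stated otherwise, and vary the effect size and the correlation. Simulations use 400,000 runs of two-sided z tests with mean shift d × √40.

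**1. Does the stated 5% reproduce?** When every null is true, any rejection is false, so the false discovery rate equals the chance of at least one rejection. For m independent tests at p < .05 this is 1 − 0.95^m:

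- m = 3: 1 − 0.95³ = 0.143
- m = 5: 1 − 0.95⁵ = 0.226

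So the 5% does not reproduce for tests with p < .05. It does for tests with q < .05, where the simulation gives 0.050 (three tests) and 0.049 (five). With some effects real, each at 80% power (shift 2.80), and independent tests:

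| Tests | Real effects | FDR among p < .05 | FDR among q < .05 |
|---|---|---|---|
| 3 | 0 | 0.143 | 0.050 |
| 3 | 1 | 0.058 | 0.033 |
| 3 | 2 | 0.021 | 0.017 |
| 5 | 0 | 0.225 | 0.049 |
| 5 | 1 | 0.114 | 0.040 |
| 5 | 2 | 0.060 | 0.030 |
| 5 | 3 | 0.031 | 0.020 |
| 5 | 4 | 0.012 | 0.010 |

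If the three Hypothesis 1 and 4 tests correlate 0.7, the all-null figures among p < .05 become 0.109 (three tests) and 0.196 (five). With one real effect they are 0.061 and 0.115. The p < .05 set falls below 5% only when most effects are real, so 5% is not a maximum for it.

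**2. Can the two rules disagree?** With ordered p-values, q(i) is the smallest of m × p(j)/j over j ≥ i.

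- p = (.04, .2, .5): 3 × .04/1 = .12, 3 × .2/2 = .30, 3 × .5/3 = .50. The first test passes p < .05 and fails q < 0.05.
- p = (.03, .04, .20): 3 × .03/1 = .09, 3 × .04/2 = .06, 3 × .20/3 = .20, so q = (.06, .06, .20). If the first two are the primaries, both are significant under the Hypothesis 1 text and neither is under the FDR text.

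**3. How often?** Probability that at least one primary has p < .05 but q ≥ .05:

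| Scenario | 0.3 SD | 0.5 SD | 0.8 SD |
|---|---|---|---|
| Three tests, all effects equal, independent | 0.162 | 0.018 | 0.000 |
| Same, correlation 0.7 | 0.135 | 0.044 | 0.0003 |
| Three tests, Hypothesis 4 null, independent | 0.226 | 0.083 | 0.001 |
| Five tests, Hypothesis 6 tests null, independent | 0.30 | 0.11 | 0.002 |

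With t tests on 39 degrees of freedom, the first row is 0.175, 0.025 and 0.000. If all three effects are null, the rules disagree on a primary in 6% of trials (5% at correlation 0.7). In that case about 64% of the p < .05 results on a given test have q ≥ .05 (52% at correlation 0.7).

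**4. Does the family matter?** Hypotheses 1 to 5 may be reported before Hypothesis 6. As a family of three, p = (.01, .03, .04) gives q = (.03, .04, .04), and all three are significant. Adding two later p-values of .2 and .5 gives 5 × .01/1 = .05 for the first and 5 × .04/3 = .067 for the other two. None is then below 0.05.

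**The case against.** The best defence is that the FDR paragraph comes last, covers every t-test, states its purpose and sets the operative criterion. Per-test thresholds followed by one overall correction are an ordinary layout. Read so, there is one verdict, and the only fault is a missing cross-reference. I agree that this is the most natural reading, but the SAP does not state it, and the Hypothesis 1 and 4 sentences are unconditional. For Hypothesis 6 the defence largely succeeds: its wording is only suggestive, so it needs the cross-reference but is not a flat contradiction.

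It can also be said that the description of the bound drives no decision and that p may be a slip for the corrected value. Correcting it would indeed change no result under the q rule, and the 14% and 23% do not show that the q rule itself has inflated error. The sentence is still false as written, and treating the FDR paragraph as governing does not cure it, because the error lies inside that paragraph.

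Finally, this is a pilot aimed mainly at estimation, p and q will both be reported, and the disagreement rates rest on assumed effects. All of that stands. It limits the harm, and it is why the rates are given as ranges.

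**Conclusion.** The concern holds on both parts. The SAP sets two thresholds for its primary outcomes without ranking them, and it misstates what the FDR procedure controls.

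That the thresholds conflict and that the bound is misplaced does not depend on any assumed effect size. How often verdicts differ does. With the three-test family, the chance of a split verdict on at least one primary runs from practically nil at 0.8 SD to 23% at 0.3 SD with Hypothesis 4 null. It is higher if the Hypothesis 6 tests join the family and are null.

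This should be corrected before analysis because it touches the primary decision rule. Reporting both p and q keeps it from being more serious.

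**What to change.** 1. In the Hypothesis 1, 4 and 6 paragraphs, replace the p < .05 criterion with a reference to the FDR rule, for example: *significance is judged by the FDR rule below (q < 0.05)*. Keep the direction and the cautious wording for Hypothesis 6.
2. Correct the description of the bound to: *the expected proportion of false positives among tests with q < 0.05 is at most 5%*.
3. As a secondary clarification, state which t-tests enter the q-values at the first report, and whether those q-values stay final when the Hypothesis 6 results arrive. Whether to use one family or two is the sponsor's choice, but step 4 of the working shows that it can change verdicts.

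The cost is SAP wording only, with no new data or tests. The one downside is that some results with p < .05 will no longer be called significant.
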